### 2.4.1.2 Other efficacy variables

The other efficacy variables are percent change from baseline in BMD at the lumbar spine, total hip, and femoral neck at the end of OL Treatment Period (Month 12) as assessed by DXA in subjects who are initially randomized to placebo in the DBPC Period and transition to romosozumab treatment for 6 months.

### Pharmacokinetic and pharmacodynamic variables 2.4.2

### Other pharmacokinetic variables 2.4.2.1

The other PK variables are as follows:

- Serum trough concentrations of romosozumab at Months 7, 9, and 12 in subjects who are continuing with 6 months of romosozumab treatment after initially being randomized to 6 months of romosozumab in the DBPC Period (a total of 12 months of romosozumab treatment).
- Serum trough concentrations of romosozumab at Months 7, 9, and 12 (1, 3, and 6 months of romosozumab exposure, respectively) in subjects who are initially randomized to placebo in the DBPC Period and transition to romosozumab treatment for 6 months. His 90chilling

Confidential

# 2.4.2.2 Other pharmacodynamic variables

The other PD variables are as follows:

- Percent changes from baseline in P1NP and sCTX at Months 7, 9, and 12 in subjects who are continuing with 6 months of romosozumab treatment after initially being randomized to 6 months of romosozumab treatment in the DBPC (a total of 12 months of romosozumab treatment).
- Percent changes from baseline in P1NP and sCTX at Months 7, 9, and 12 (1, 3, and 6 months of romosozumab exposure, respectively) in subjects who are initially randomized to placebo in the DBPC Period and transition to romosozumab treatment for 6 months.
- AUC for the entire 12-month treatment period for P1NP in subjects who are continuing with 6 months of romosozumab treatment after initially being randomized to 6 months of romosozumab treatment in the DBPC Period (for a total of 12 months of romosozumab treatment).

# 2.4.3 Safety variables

The safety variables listed below will be assessed during the OL Treatment Period, including some selected safety variables that will be followed up to Month 15, in subjects who are initially randomized to 6 months of romosozumab treatment in the DBPC Period and continue with romosozumab for 6 months (for a total of 12 months of romosozumab treatment) and in subjects who are initially randomized to placebo in the DBPC Period and transition to romosozumab treatment for 6 months.

# 2.4.3.1 Primary safety variable

The primary safety variable is the overall incidence of TEAEs.

# 2.4.3.2 Other safety variables

The other safety variables are as follows:

- Changes from baseline in laboratory assessments (serum chemistry and hematology) and shifts from baseline to the worst value between baseline and Month 12.
- Changes from baseline in vital signs.
- Changes from baseline in ECG parameters.
- Clinically significant physical examination findings from baseline through Month 12.
- Incidence of subjects with antiromosozumab antibodies at Months 7, 9, and 12, and at the EOS Visit.

# 2.5 Study design and conduct

This is a Phase 3 multicenter randomized, DBPC study followed by OL Treatment Period in postmenopausal Chinese women with osteoporosis to evaluate the efficacy, safety and tolerability of romosozumab treatment. The study consists of 4 study periods: Screening Period (Day -35 to Day -1), 6-month DBPC period, 6-month OL Treatment Period, and 3-month FU Period. The overall study design including treatment assignments is depicted in the schematic diagram in Figure 1. For each individual subject, the study will last approximately 16 months. A

03 Mar 2023 OP0002

subject's participation in the study may be extended up to 1 year after the final IMP administration if the subject tests positive for neutralizing antibodies to romosozumab at the EOS Visit or ET Visit.

[figure not shown]
In the DBPC Period, after screening, approximately 300 subjects will be randomized, stratified by age (<75 years,  $\ge 75$  years), in a 2:1 ratio to receive either 210 mg romosozumab subcutaneous (sc) treatment every month (OM) (200 subjects) or matched placebo sc OM (100 subjects) in a blinded manner for 6 months to evaluate if romosozumab treatment for 6 months. compared with placebo, is effective in increasing BMD, as assessed by DXA, at the lumbar spine, total hip, and femoral neck. The primary analysis will be performed using the data obtained from the DBPC Period.

Upon completion of the 6-month DBPC Period, subjects will enter the 6-month OL Treatment Period and receive 210mg romosozumab sc QM for 6 months in an open-label fashion. During this period, all subjects will receive active treatment (romosozumab), 12 months exposure for subjects randomised to romosozumab and 6 months exposure for those randomized to placebo.

After completing the OL Treatment period, subjects will be followed up for an additional 3 months (FU Period) and will complete the EOS Visit (Month 15). Subject participation in the study is concluded after the EOS Visit. Subjects who test positive for neutralizing antibodies to romosozumab at the EOS Visit or ET Visit will be asked to return for additional follow-up testing for up to 1 year after final administration of investigational medicinal product (IMP).

# 2.6 Determination of sample size

The sample size calculations were done using historical BMD data of all 3 anatomical sites taken into account from the romosozumab studies 20070337 and 20120156.

• Assumptions for BMD of the lumbar spine:

Postmenopausal women with osteoporosis in 20120156 showed a treatment difference of 8.4 with 95% CI: 6.9 to 9.9 when compared with placebo BMD response at lumbar spine. Furthermore, postmenopausal women with osteoporosis in 20070337 showed a treatment difference of 9.4 (95% CI: 7.9 to 10.8). Taking the minimum of the lower confidence bound (conservative approach) results in an assumption of 6.9 for the treatment difference in percentage change from baseline at Month 6.

For postmenopausal women with osteoporosis in 20120156, the upper bounds of the SDs were 4.94 for the romosozumab group and 3.93 for the placebo group; in 20070337, the upper bounds of the SDs were 6.10 and 3.32, respectively. This indicates that SDs were differing between romosozumab and placebo necessitating a statistical test accounting for differing SDs. To merge the SDs of 20070337 and 20120156, the pooled common SDs were calculated separately for romosozumab and placebo taking the upper bound in each study and each arm (conservative approach). As a result, the assumptions for the SDs are 5.26 for the romosozumab arm and 3.34 for the placebo arm.

Assumptions for BMD of the total hip

Studies 20070337 and 20120156 showed a minimum treatment difference on total hip BMD of 3.5 (95% CI: 2.5 to 4.4) when compared with placebo. The combined upper bounds of the SDs for 20070337 and 20120156 were 3.80 for the romosozumab group and 3.03 for the placebo group.

## • Assumptions for BMD of the femoral neck:

Studies 20070337 and 20120156 showed a minimum treatment difference on femoral neck BMD of 3.2 (95% CI: 2.0 to 4.3) when compared with placebo. The combined upper bounds of the SDs for 20070337 and 20120156 were 4.39 for the romosozumab group and 4.10 for the placebo group.

# • Resulting sample size:

For the sample size calculations, a 2-group Satterthwaite t-test will be assumed (2-sided on a 5% significance level) which allows for unequal SDs and unequal sample size ratios. Taking into account the upper bounds pooled common SDs and the minimum effect size as assumptions (BMD of the femoral neck outlined above), the sample size of 146 subjects for romosozumab and 73 subjects for placebo would preserve at least 90% power for the percent change from baseline in BMD of the lumbar spine, total hip and femoral neck at Month 6.

To give a reasonable chance to show significance, at least 90% power for all 3 anatomical sites, following a hierarchical testing procedure (see Section 4.5) with safety objectives and dropout taken into account, a total sample size of 300 subjects (ie, 200 subjects in the romosozumab group and 100 subjects in the placebo group) seemed appropriate.

# 3 DATA ANALYSIS CONSIDERATIONS

# 3.1 General presentation of summaries and analyses

Statistical evaluation will be performed by the biostatistics department at UCB and/or Parexel. All computations will be performed using SAS® version 9.4 or later (SAS Institute, NC, USA).

Summary statistics will consist of frequency tables for categorical variables. For continuous variables, descriptive statistics (number of available observations, mean, median, SD, minimum and maximum, coefficient of variance (CV) [where applicable]) will be tabulated. Data may be summarized by treatment group and in addition, may be summarized by time (using defined analysis visit windows, referring to section 3.2.3).

Unless otherwise noted, all summaries will be displayed by randomized treatment group (placebo, romosozumab 210mg sc QM) regardless of the treatment individual subjects actually received. A summary with all treatment groups combined (ie, total column) will be presented for the demographic and Baseline characteristics, for the prior medications, as well as for the medical, procedure history and risk factors.

Decimal places for descriptive statistics will always apply the following rules:

- "n" or "N" will be an integer.
- Percentage values will be presented with 1 decimal place. No percentage will be displayed for zero counts and no decimal will be displayed when percentage is 100%.
- Mean, SD, and median will use 1 additional decimal place compared to the original data.

Confidential Page 16 of 89

- CV (%) will be presented with 1 decimal place.
- Minimum and maximum will have the same number of decimal places as the original value.
- Categorical missing data will be summarized in a separate category.

Statistical tests of efficacy variables will be presented as 2-sided p-values rounded to 3 decimal places. P-values less than 0.001 will be presented as "<0.001" and p-values greater than 0.999 will be presented as ">0.999." The multiple testing issues for the primary and secondary efficacy analyses are handled with a fixed sequence testing procedure as described in Section 4.5.

The SAS outputs supportive of any statistical model (ie. all excluding the descriptive analyses) will be provided as a separate Portable Document Format (PDF) document in addition to Tables, Figures and Listings (TFLs). These outputs will be included in the "Documentation of Statistical Methods" section of the clinical study report.

The order of treatment groups to be presented in tables from left to right will be: Outputs including only data of the DBPC Period for 6-Month Analysis:

- Placebo
- Romosozumab 210mg

Outputs including also data of the OLE Treatment Period and FU Period for Final Analysis:

- Placebo / Romosozumab 210mg (subjects receive Placebo during 6-month DBPC Period and then receive Romosozumab during OLE Period)
- Romosozumab 210mg / Romosozumab 210mg (subjects receive Romosozumab during 6-month DBPC Period and then receive Romosozumab during OLE Period)

Data listings will be prepared for subjects with available data including the calculated data [Enrolled Set (ES), Randomized Set (RS), Safety Set (SS), Full Analysis set (FAS), Per-Protocol Set (PPS), Pharmacokinetic Per-Protocol Set (PK-PPS) and Pharmacodynamic Per-Protocol Set (PD-PPS)], depending on the domain.

# 3.2 General study level definitions

# 3.2.1 Analysis time points

# 3.2.1.1 6-month analysis

The 6-month analysis of efficacy and safety will be performed after all subjects have completed the 6-month DBPC Period. After the last subject last visit of the 6-month DBPC Period and after data cleaning, a database snapshot will be taken for the 6-month analysis. Following the snapshot, the study will be unblinded to the individuals of the dedicated team from sponsor and CRO involved in conducting the statistical analysis and in the compilation of the statistical analysis report and the CSR. The names of members of the dedicated team will be documented before the database snapshot. The investigators and other sponsor staff initially remain blinded. Upon finalization of the CSR (6-month analysis), investigators will remain blinded to treatment assignments for study participants in their sites. The leading Principal Investigator (PI) involved in the sign-off of the CSR (6-month analysis) will be unblinded at the aggregate level (tables and

Confidential Page 17 of 89

figures) but will remain blinded to treatment assignment for individual study participants. Other investigators will remain blinded at the aggregate level to the 6-month results until the final analysis of the data. Note this is a change from the protocol as regulatory requirements now only require the leading PI to sign-off the CSR. Subjects will remain blinded to the DBPC Period treatment assignment throughout the study.

The primary variable of the 6-month analysis is the evaluation of the effect of treatment with romosozumab compared with placebo on the percent change in BMD at the lumbar spine in postmenopausal Chinese women with osteoporosis. Formal statistical testing will be performed (see Section 4.5).

The secondary variables of the 6-month analysis are to evaluate the effects of treatment with romosozumab compared with placebo on the percent change in BMD at the total hip and femoral neck. For these endpoints, confirmatory testing will be performed as outlined in Section 4.5.

Other variables of the 6-month analysis include the evaluation of the effect of treatment with romosozumab compared with placebo at 3 months on the percent change in BMD at the lumbar spine, total hip and femoral neck, the evaluation of the effect of treatment with romosozumab compared with placebo at 1-, 3-, and 6-month time points on the percent changes in BTMs, and to characterize serum concentrations of romosozumab in subjects who are randomized to romosozumab for 6 months. For the other variables, statistical testing will be performed in an exploratory manner.

The safety analyses of the 6-month analysis will compare the safety of romosozumab treatment with placebo in postmenopausal Chinese women with osteoporosis. The safety analyses in the 6-month analysis will include all available data collected up to the time of 6-month data snapshot. The safety variables to be analyzed in the 6-month analysis are presented in Section 2.3.3.

# 3.2.1.2 Final analysis

After all subjects have the opportunity to complete the Month 15 Visit, the database lock will be executed. Based on these data, the remaining efficacy and safety analyses for Month 12 and the safety analyses for the overall study period (treatment start through Month 15) will be performed.

# 3.2.2 Relative day

Days on or after the day of first dose of IMP and prior to or on the day of last IMP:

Relative day will be calculated as the current date minus the date of first dose of IMP + 1 (eg. the day of first dose will be Day 1).

# Days prior to the first dose of IMP:

Relative day will be calculated as date of first dose of study drug minus the current date (the day prior to first dose will be Day -1).

### Days after the last dose of IMP:

Relative day will be calculated as the current date minus the date of last dose of study drug including a "+" to denote posttreatment days (eg, the day after the last dose will be Day +1). Relative day will not be calculated for partial dates.

# 3.2.3 Analysis visit windows

For the Baseline assessment and definition, please refer to Section 3.3 for details. For the post-baseline assessment, if more than 1 visit measurement falls within the defined visit window, the result from the visit closest to the target day will be used for analysis and summarization. If 2 evaluations are of the same distance from the target day, the result from the later visit will be used. Scheduled and unscheduled visits/measurements are considered for this purpose. To allow for variations in scheduling, the following visit windows will be used to assign evaluations to a most appropriate nominal visit for analysis and summarization. Furthermore, there will be no gaps between visit windows in order to include as many data points as possible for summarization.

## **DXA Scans**

Nominal visit	Target study day	Window Definition (Study Day)
Baseline	1	Last evaluation prior to first dose of IMP
Month 3	90	Day 2 – 135
Month 6	180	Day 136 - End of DBPC period + 14 days
Month 12	360	≥ Day End of DBPC period + 15

# BTMs (serum CTX and P1NP), PK samples, antibodies samples and laboratory tests

Nominal visit	Target study day	Window Definition (Study Day)
Baseline	1	Last evaluation prior to or on Study Day 1 and prior to the first IMP
Month 1	30	Day 2 – 60
Month 3	90	Day 61 – 135
Month 6	180	Day 136 – End of DBPC period (note: M6 IMP will belong to OL)
Month 7	210	Day End of DBPC period + 1 – 240
Month 9	270	Day 241-315
Month 12	360	≥ Day 316

Confidential Page 19 of 89

# Vital signs

Nominal visit	Target study day	Window Definition (Study Day)
Baseline	1	Last evaluation prior to or on Study Day 1 prior to the first IMP
Month 1	30	Day 2 – 105
Month 6	180	Day 106 – End of DBPC period
Month 7	210	Day End of DBPC period + 1 – 285
Month 12	360	≥ Day 286

## **ECG**

Nominal visit	Target study day	Window Definition (Study Day)
Baseline	1	Last evaluation prior to or on Study Day 1 prior to the first IMP
Month 1	30	Day 2 – 60
Month 3	90	Day 61 – 135
Month 6	180	Day 136 – End of DBPC period
Month 9	270	Day End of DBPC period + 1 - 315
Month 12	360	≥ Day 316

The definition for End of Study, End of DBPC period, End of OL Period and End of Follow-Up Period are specified in Section 3.2.4.

# Timing of analysis cut-offs End of study date

End of study (EOS) date is defined as the date of the last contact; or the date of the last assessment for the early termination (ET) visit for subjects who discontinued the study if no last contact date in EDC CRF form.

### 3.2.4.2 End of DBPC Period date

End of DBPC Period date is defined as the last date of the assessments of the Month 6 visit or start date of OL visits if Month 6 visit is missed. For subjects who discontinued from the study before completing Month 6, the ET date is used for the end of DBPC period date. -204g4

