6.3.1 Withdrawal of IMP

Subjects can decide to discontinue IMP but continue participation in the study. If IMP is. discontinued, the investigator should encourage the subject to continue participation by attending scheduled study visits to have procedures/assessments performed and data collected including endpoints and AEs. The investigator must document any changes to the scheduled visits and assessments (Table 5–1) and the plan for follow up that is agreed by the subject.

Subjects might have IMP withdrawn if any of the following events occur (but not limited to):

- Subject request.
- Decision of the sponsor or investigator.
- Safety concern (eg., due to an AE, ineligibility determined, protocol deviation, noncompliance, requirement for alternative therapy, protocol-specified criteria).
- Clinical fracture or BMD decrease from baseline of 7% or more at the lumbar spine, total hip, or femoral neck.

In the event that a subject experiences a clinical fracture or a BMD decrease from baseline of 7% or more at the lumbar spine, total hip or femoral neck at any time during the study, the investigator is required to discuss the subject's individual fracture risk and alternative treatment options with the subject and to note the discussion in the subject's records. If a decision is made to begin an alternative approved therapy, the subjects must discontinue IMP and every effort should be made to have the subject complete the remaining study visits and assessments.

Withdrawal from study 6.3.2

Subjects can be withdrawn from the study if any of the following events occur:

- Subject develops a serious illness that would interfere with her continued participation.
- Subject is noncompliant with the study procedures or medications in the opinion of the investigator.
- Subject withdraws her consent.
- There is confirmation of a pregnancy during the study, as evidenced by a positive pregnancy test.
- The sponsor or a regulatory agency requests withdrawal of the subject.

Withdrawal of consent for a study means that the subject does not wish to continue in the study. Subject data up to withdrawal of consent will be included in the analysis of the study.

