Subjects who withdraw from the study should complete the ET Visit. Refer to the schedule of assessments for the procedures to be performed at this visit (Table 5–1). These subjects will be encouraged to return to the study site to complete the procedures and assessments for the EOS Visit, 4 months after the final administration of IMP.

Investigators should attempt to obtain information on subjects in the case of withdrawal or discontinuation. For subjects considered as lost to follow up, the investigator should make an effort (at least 1 phone call and 1 written message to the subject), and document his/her effort (date and summary of the phone call and copy of the written message in the source documents), to complete the final evaluation. All results of these evaluations and observations, together with a narrative description of the reason(s) for removing the subject, must be recorded in the source documents. The eCRF must document the primary reason for withdrawal.

Subjects who withdraw from the study will not be replaced.

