#### Adverse events c 10.2

Treatment emergent AEs (TEAE) are defined as all AEs started or worsened in severity on or after the date of receiving first dose of IMP and before EOS date except lipid-type AEs starting on the date of first dose of IMP and not worsening (and not deemed IMP related by the investigator). Lipid-type AEs will be defined by the Dyslipidaemia SMQ (see Appendix 13.7). The different handling of lipid-type AEs starting on the date of first dose of IMP is to ensure that pre-existing lipid abnormalities are not reported as TEAEs (lipids are only measured at Day 1 before first IMP and not at Screening).

All subsequently described displays in Section 10.2 will be compiled for the DBPC Period and for the overall study period (treatment start through Month 15). For the displays on the DBPC Period, TEAEs with a start date before or on the End of DBPC period date will be included. For the overall period, TEAEs with a start date before or on the EOS date will be included.

Duration of AEs will not be calculated if there is missing stop date information. If the intensity of an AE is unknown, it is considered as severe. If the relationship to study drug is missing, it is considered as related. Note that if the seriousness of an adverse event is unknown, every attempt should be made to resolve this prior to a snapshot for an interim analysis or database lock; in the exceptional case that the seriousness of an adverse event is still missing then no imputation should be applied for this characteristic.

If a TEAE occurs on the date of switch from the DBPC period to the OL period, the event is attributed to the DBPC treatment. The only exception that TEAEs of injection site reactions (see Appendix 13.5), potentially related to hypersensitivity (Standardized MedDRA® Query [SMQ], narrow scope) will be in OL period.

The number and incidence of TEAEs will be summarized by treatment group, the MedDRA® SOC and PT with the SOC sorted alphabetically and within SOC the PT sorted by descending order of frequencies. The incidence of TEAEs will also be summarized by treatment group (including romosozumab total), intensity and relationship to IMP.

Adverse events will be presented as "number of participants (percentage of participants) [number of events]". In this style of output, "[number of events]" will include all cases of an AE including repeat occurrences in individual participants, while "number of participants" will count each participant only once.

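### Double-blind TEAE counting stops at the ET visit for women who leave the study but runs to Month 6 for women who only stop IMP, so new events after ET miss the placebo-controlled tables

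*SAP*

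**What the plan says.** Three rules in the SAP interact.

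- **SAP 3.2.4.2, women still in the study:** "End of DBPC Period date is defined as the last date of the assessments of the Month 6 visit", or the start of open-label visits if Month 6 is missed. Women who stop IMP but keep attending (Protocol 6.3.1) fall here.
- **SAP 3.2.4.2, women who left the study** "before completing Month 6, the ET date is used for the end of DBPC period date".
- **SAP 10.2:** "For the displays on the DBPC Period, TEAEs with a start date before or on the End of DBPC period date will be included". By contrast, "For the overall period, TEAEs with a start date before or on the EOS date will be included", and SAP 3.2.4.1 states "End of study (EOS) date is defined as the date of the last contact".

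The protocol plans AE collection after ET. Withdrawn women are "encouraged to return to the study site to complete the procedures and assessments for the EOS Visit, 4 months after the final administration of IMP" (Protocol 6.3.2). AEs are recorded at that visit (8.4.1), and AE follow-up usually lasts 4 months after IMP stops (11.1.3).

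SAP 10.2 says that its displays are produced for both the double-blind and the overall period. They include adjudicated CV events, reported with odds ratios and 95% confidence intervals (10.2.4.3).

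**The concern.** A woman who withdraws before Month 6 and takes no open-label dose stays in her randomized condition throughout. An event that starts after her ET visit is still a TEAE, because the definition runs to last contact. It is nevertheless kept out of the only tables that compare romosozumab with placebo. The same event on the same day is counted if the woman stopped IMP but stayed in the study.

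The cut-off follows no single principle. An on-treatment rule would also stop counting women who discontinue IMP and stay. A rule using all available data would count withdrawn women as far as they were observed. SAP 4.2 includes data regardless of IMP discontinuation, and SAP 3.2.1.1 says the 6-month safety analyses use everything collected up to the snapshot. Neither sentence is reconciled with the specific cut-off in 10.2.

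The overall tables do not fill the gap. Their columns are placebo/romosozumab and romosozumab/romosozumab (SAP 3.1). Time at risk starts at the first romosozumab dose (10.2.1), so a placebo woman who left early has no defined person-time there. The double-blind tables listed in 10.2.3 are not expressed per 100 patient-years, so they do not show the shorter coverage.

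**Working it through.** No figure in the plan depends on this rule, so there is nothing to reproduce. The check traces the dates and then sizes the excluded time.

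**Tracing the rule.** Take a last dose on Day 61, ET on Day 75, and an AE that starts on Day 110 and is reported at the EOS visit on Day 61 + 120 = 181.

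- Woman who left the study: the cut-off is Day 75. Since 110 > 75, the AE is excluded from the double-blind tables and included in the overall tables.
- Woman who stopped IMP on Day 75 and attended Month 6 on Day 180: since 110 ≤ 180, the AE is included.

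**Inputs from the documents.** A month is 30 days (Protocol 8), which puts doses on Days 1, 31, 61, 91, 121 and 151. The EOS visit is 120 days after the last dose (Protocol 6.3.2). There are 300 women (SAP 2.6).

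**Assumptions, not in the documents.** Withdrawal is uniform over Days 2 to 180. ET falls 0, 14 or 28 days later, capped at Day 180. Every withdrawn woman attends EOS. Withdrawal before Month 6 is 5%.

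**Formula.** Excluded days = min(180, last dose + 120) − ET day, not below 0.

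| Last dose (day) | Withdrawal days | Latest countable day | Mean excluded days, ET delay 0 / 14 / 28 |
|---|---|---|---|
| 1 | 2–30 | 121 | 105 / 91 / 77 |
| 31 | 31–60 | 151 | 105.5 / 91.5 / 77.5 |
| 61 | 61–90 | 180 | 104.5 / 90.5 / 76.5 |
| 91 | 91–120 | 180 | 74.5 / 60.5 / 46.5 |
| 121 | 121–150 | 180 | 44.5 / 30.5 / 16.5 |
| 151 | 151–180 | 180 | 14.5 / 4.0 / 0.03 |
| All 179 days | | | **74.6 / 61.2 / 48.8** |

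**Share of planned double-blind time** = withdrawal rate × mean excluded days / 180. At 5% this is 0.05 × 74.6/180 = 2.1%, 0.05 × 61.2/180 = 1.7% and 0.05 × 48.8/180 = 1.4%. If half the women return, these become 1.0%, 0.9% and 0.7%.

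**Cross-check with a simpler model.** Let exit follow each of the six doses with equal probability, with ET 30 days after the last dose. Excluded days are 90, 90, 90, 60, 30 and 0 (mean 60), and counted days average 105. At 5% withdrawal, 0.05 × 60/180 = 1.7%, which agrees.

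**Events.** With ET at 14 days, 15 withdrawals × 61.2 / 365.25 = 2.5 person-years over both arms. At an assumed 2 AEs per person-year that is about 5 events; at 0.1 per person-year it is about 0.25. For CV events, Protocol 2.2 gives 0.8% each for serious cardiac ischemic and cerebrovascular events at 12 months on romosozumab in study 20110142. Adding them as an upper assumption gives 0.016 per person-year, and 2.5 × 0.016 = 0.04 events. If one did occur, it would be 1/100 = 1% of the placebo arm or 1/200 = 0.5% of the romosozumab arm.

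**The case against.** Closing the period at study exit is a defensible convention, and SAP 3.2.4.4 does the same for the open-label period. The rule is identical in both arms, and withdrawal happens under blinding. Safety is descriptive with no planned tests (SAP 10.2.3). Withdrawals and their reasons are tabulated by arm through Month 6 (SAP 5.1), so an imbalance would be partly visible. All of this stands, and it limits the consequence.

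Three stronger readings are tempting, but the documents do not support them.

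- *The events are lost.* They are not. They stay in the overall-period displays, and the DMC reviews unblinded safety data (SAP 4.3).
- *The rule removes events in the women most likely to have them.* Protocol 6.3.2 does list "Subject develops a serious illness that would interfere with her continued participation" as a reason to withdraw, but it is one of five. The illness that prompts withdrawal normally starts before ET, where AEs are recorded, so it is already counted. Only new events after ET are affected.
- *Over 40% of withdrawn women's collected time is discarded.* Leaving exit after dose 6 out of the simpler model gives mean excluded days of 72 against 90 counted, and 72/162 = 44%. With dose 6 included it is 60/165 = 36%. Both figures are ceilings. EOS attendance is only encouraged, and data after withdrawal of consent are not used (Protocol 6.3.2). With half returning, the 44% becomes 36/126 = 29%.

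Changing the cut-off also has limits. Women who do not return would still stop near ET. Events would be recalled at one visit instead of at monthly visits. Some could follow other osteoporosis therapy, because the protocol's prohibition ends 1 month after study medication stops early (7.8.2).

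**Conclusion.** The inconsistency is real and follows directly from the date rules: double-blind AE coverage depends on how a woman stops, and new events after ET are left out of the placebo-controlled displays. The effect is small. With full EOS attendance the ceiling is about 50 to 75 days per early withdrawal, or about 1.4% to 2.1% of planned double-blind time at 5% withdrawal, and about half that if half return. The withdrawal rate, ET timing, attendance and event rates are all assumptions.

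A reader might infer that the randomized safety comparison is biased. That would need withdrawal, or event risk after withdrawal, to differ by arm, and the documents give no evidence on either. If neither differs, counts are slightly low in both arms. No error rate or formal conclusion changes. Severity is minor; the point is worth making because the correction is cheap.

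There is a related gap. SAP 3.2.4.2 gives no end date for a withdrawn woman with no ET visit, for example after death or loss to follow-up, yet SAP 10.2.3 plans double-blind tables of TEAEs leading to death.

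**What to change.** Add one sentence to SAP 10.2. For women who leave the study before Month 6 without an open-label dose, the DBPC adverse event displays include all TEAEs and adjudicated events starting up to the earlier of last contact and Day 180. Keep the ET date in SAP 3.2.4.2 for visit windows only. State in SAP 3.2.1.1 that its all-available-data sentence is subject to this cut-off.

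Using last contact also supplies a date for withdrawn women without an ET visit, and it respects withdrawal of consent. No new data collection is needed.

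The cost is that a few off-drug events enter the double-blind tables, as already happens for women who stop IMP and stay. Some will be recalled at a single visit, and some may follow other therapy. Coverage will still depend on who returns, so show double-blind observation time by arm next to the TEAE tables.
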